14.1.17 Time to event variables

14.1.18 Progression-free survival

Usually in all Oncology studies, patients are followed for tumor progression after discontinuation of study medication for reasons other than progression or death. If this is not used, e.g. in Phase I or II studies, this should be clearly stated in the protocol. Note that randomized trials (preferably blinded) are recommended where PFS is to be the primary endpoint.

Progression-free survival (PFS) is the time from date of randomization/start of treatment to the date of event defined as the first documented progression or death due to any cause. If a patient has not had an event, progression-free survival is censored at the date of last adequate tumor assessment.

14.1.19 Overall survival

All patients should be followed until death or until patient has had adequate follow-up time as specified in the protocol whichever comes first. The follow-up data should contain the date the patient was last seen alive / last known date patient alive, the date of death and the reason of death (“Study indication” or “Other”).

Overall survival (OS) is defined as the time from date of randomization/start of treatment to date of death due to any cause. If a patient is not known to have died, survival will be censored at the date of last known date patient alive.

14.1.20 Time to progression

[figure not shown]
Some studies might consider only death related to underlying cancer as an event which indicates progression. In this case the variable “Time to progression” might be used. TTP is defined as PFS except for death unrelated to underlying cancer.

Time to progression (TTP) is the time from date of randomization/start of treatment to the date of event defined as the first documented progression or death due to underlying cancer. If a patient has not had an event, time to progression is censored at the date of last adequate tumor assessment.

14.1.21 Time to treatment failure

This endpoint is often appropriate in studies of advanced disease where early discontinuation is typically related to intolerance of the study drug. In some protocols, time to treatment failure may be considered as a sensitivity analysis for time to progression. The list of discontinuation reasons to be considered or not as treatment failure may be adapted according to the specificities of the study or the disease.

Time to treatment failure (TTF) is the time from date of randomization/start of treatment to the earliest of date of progression, date of death due to any cause, or date of discontinuation due to reasons other than ‘Protocol violation’ or ‘Administrative problems’. The time to treatment failure for patients who did not experience treatment failure will be censored at last adequate tumor assessment.

14.1.22 Duration of response

The analysis of the following variables should be performed with much caution when restricted to responders since treatment bias could have been introduced. There have been reports where a treatment with a significantly higher response rate had a significantly shorter duration of response but where this probably primarily reflected selection bias which is explained as follows: It is postulated that there are two groups of patients: a good risk group and a poor risk group. Good risk patients tend to get into response readily (and relatively quickly) and tend to remain in response after they have a response. Poor risk patients tend to be difficult to achieve a response, may have a longer time to respond, and tend to relapse quickly when they do respond. Potent agents induce a response in both good risk and poor risk patients. Less potent agents induce a response mainly in good risk patients only. This is described in more detail by Morgan (1988)

It is recommended that an analysis of all patients (both responders and non-responders) be performed whether or not a “responders only” descriptive analysis is presented. An analysis of responders should only be performed to provide descriptive statistics and even then interpreted with caution by evaluating the results in the context of the observed response rate

If an inferential comparison between treatments is required this should only be performed on all patients (i.e. not restricting to “responders” only) using appropriate statistical methods such as the techniques described in Ellis et al (2008). It should also be stated in the protocol if duration of response is to be calculated in addition for unconfirmed response.

For summary statistics on “responders” only the following definitions are appropriate.

(Specific definitions for an all-patient analysis of these endpoints are not appropriate since the status of patients throughout the study is usually taken into account in the analysis).

Duration of overall response (CR or PR): For patients with a CR or PR (which may have to be confirmed the start date is the date of first documented response (CR or PR) and the end date and censoring is defined the same as that for time to progression.

[figure not shown]
The following two durations might be calculated in addition for a large Phase III study in which a reasonable number of responders is seen.

Duration of overall complete response (CR): For patients with a CR (which may have to be confirmed) the start date is the date of first documented CR and the end date and censoring is defined the same as that for time to progression.

Duration of stable disease (CR/PR/SD): For patients with a CR or PR (which may have to be confirmed) or SD the start and end date as well as censoring is defined the same as that for time to progression.

14.1.23 Time to response

Time to overall response (CR or PR) is the time between date of randomization/start of treatment until first documented response (CR or PR). The response may need to be confirmed depending on the type of study and its importance. Where the response needs to be confirmed then time to response is the time to the first CR or PR observed.

Although an analysis on the full population is preferred a descriptive analysis may be performed on the “responders” subset only, in which case the results should be interpreted with caution and in the context of the overall response rates, since the same kind of selection bias may be introduced as described for duration of response in Section 14.4.22. It is recommended that an analysis of all patients (both responders and non-responders) be performed whether or not a “responders only” descriptive analysis is presented. Where an inferential statistical comparison is required, then all patients should definitely be included in the analysis to ensure the statistical test is valid. For analysis including all patients, patients who did not achieve a response (which may have to be a confirmed response) will be censored using one of the following options.

- at maximum follow-up (i.e. FPFV to LPLV used for the analysis) for patients who had a PFS event (i.e. progressed or died due to any cause). In this case the PFS event is the worst possible outcome as it means the patient cannot subsequently respond. Since the statistical analysis usually makes use of the ranking of times to response it is sufficient to assign the worst possible censoring time which could be observed in the study which is equal to the maximum follow-up time (i.e. time from FPFV to LPLV)
- at last adequate tumor assessment date otherwise. In this case patients have not yet progressed so they theoretically still have a chance of responding

Time to overall complete response (CR) is the time between dates of randomization/start of treatment until first documented CR. Similar analysis considerations including (if appropriate) censoring rules apply for this endpoint described for the time to overall response endpoint.

14.1.24 Definition of start and end dates for time to event variables

Assessment date

For each assessment (i.e. evaluation number), the **assessment date** is calculated as the latest of all measurement dates (e.g. X-ray, CT-scan) if the overall lesion response at that assessment is CR/PR/SD/UNK. Otherwise - if overall lesion response is progression – the assessment date is calculated as the earliest date of all measurement dates at that evaluation number.

Start dates

[figure not shown]
For all “time to event” variables, other than duration of response, the randomization/ date of treatment start will be used as the start date.

For the calculation of duration of response the following start date should be used:

- Date of first documented response is the assessment date of the first overall lesion response of CR (for duration of overall complete response) or CR / PR (for duration of overall response) respectively, when this status is later confirmed.

End dates

The end dates which are used to calculate ‘time to event’ variables are defined as follows:

- Date of death (during treatment as recorded on the treatment completion page or during follow-up as recorded on the study evaluation completion page or the survival follow-up page).
- Date of progression is the first assessment date at which the overall lesion response was recorded as progressive disease.
- Date of last adequate tumor assessment is the date the last tumor assessment with overall lesion response of CR, PR or SD which was made before an event or a censoring reason occurred. In this case the last tumor evaluation date at that assessment is used. If no postbaseline assessments are available (before an event or a censoring reason occurred) the date of randomization/start of treatment is used.
- Date of next scheduled assessment is the date of the last adequate tumor assessment plus the protocol specified time interval for assessments. This date may be used if back-dating is considered when the event occurred beyond the acceptable time window for the next tumor assessment as per protocol (see [Section 14.1.25](#)).

Example (if protocol defined schedule of assessments is 3 months): tumor assessments at baseline - 3 months - 6 months - missing - missing - PD. Date of next scheduled assessment would then correspond to 9 months.

- Date of discontinuation is the date of the end of treatment visit.
- Date of last contact is defined as the last date the patient was known to be alive. This corresponds to the latest date for either the visit date, lab sample date or tumor assessment date. If available, the last known date patient alive from the survival follow-up page is used. If no survival follow-up is available, the date of discontinuation is used as last contact date.
- Date of secondary anti-cancer therapy is defined as the start date of any additional (secondary) antineoplastic therapy or surgery.

14.1.25 Handling of patients with non-measurable disease only at baseline

[figure not shown]
It is possible that patients with only non-measurable disease present at baseline are entered into the study, either because of a protocol violation or by design (e.g. in Phase III studies with PFS as the primary endpoint). In such cases the handling of the response data requires special consideration with respect to inclusion in any analysis of endpoints based on the overall response evaluations.

It is recommended that any patients with only non-measurable disease at baseline should be included in the main (ITT) analysis of each of these endpoints.

Although the text of the definitions described in the previous sections primarily relates to patients with measurable disease at baseline, patients without measurable disease should also be incorporated in an appropriate manner. The overall response for patients with measurable disease is derived slightly differently according to [Table 14-4](#).

Table 14-4 Overall lesion response at each assessment: patients with non-target disease only

Non-target lesions	New Lesions	Overall lesion response
CR	No	CR

Non-CR/Non-PD ¹	No	Non-CR/non-PD
UNK	No	UNK
PD	Yes or No	PD
Any	Yes	PD
¹ As defined in Section 14.1.7 .		

In general, the **non-CR/non-PD response** for these patients is considered equivalent to an SD response in endpoint determination. In summary tables for best overall response patients with only non-measurable disease may be highlighted in an appropriate fashion e.g. in particular by displaying the specific numbers with the non-CR/non-PD category.

In considering how to incorporate data from these patients into the analysis the importance to each endpoint of being able to identify a PR and/or to determine the occurrence and timing of progression needs to be taken into account.

For ORR it is recommended that the main (ITT) analysis includes data from patients with only non-measurable disease at baseline, handling patients with a best response of CR as “responders” with respect to ORR and all other patients as “non-responders”.

For PFS, it is again recommended that the main ITT analyses on these endpoints include all patients with only non-measurable disease at baseline, with possible sensitivity analyses which exclude these particular patients. Endpoints such as PFS which are reliant on the determination and/or timing of progression can incorporate data from patients with only nonmeasurable disease.

14.1.26 Sensitivity analyses

This section outlines the possible event and censoring dates for progression, as well as addresses the issues of missing tumor assessments during the study. For instance, if one or more assessment visits are missed prior to the progression event, to what date should the progression event be assigned? And should progression event be ignored if it occurred after a long period of a patient being lost to follow-up? It is important that the protocol and RAP specify the primary analysis in detail with respect to the definition of event and censoring dates and also include a description of one or more sensitivity analyses to be performed.

Based on definitions outlined in [Section 14.1.24](#), and using the draft FDA guideline on endpoints (Clinical Trial Endpoints for the Approval of Cancer Drugs and Biologics, April 2005) as a reference, the following analyses can be considered:

[figure not shown]

Table 14-5 Options for event dates used in PFS, TTP, duration of response

Situation		Options for end-date (progression or censoring) ¹ (1) = default unless specified differently in the protocol or RAP	Outcome
A	No baseline assessment	(1) Date of randomization/start of treatment ³	Censored
B	Progression at or before next scheduled assessment	(1) Date of progression (2) Date of next scheduled assessment ²	Progressed Progressed
C1	Progression or death after exactly one missing assessment	(1) Date of progression (or death) (2) Date of next scheduled assessment ²	Progressed Progressed
C2	Progression or death after two or more missing assessments	(1) Date of last adequate assessment ² (2) Date of next scheduled assessment ² (3) Date of progression (or death)	Censored Progressed Progressed
D	No progression	(1) Date of last adequate assessment	Censored
E	Treatment discontinuation due to 'Disease progression' without documented progression, i.e. clinical progression based on investigator claim	(1) N/A (2) Date of discontinuation (visit date at which clinical progression was determined)	Ignored Progressed
F	New anticancer therapy given	(1) Date of last adequate assessment (2) Date of secondary anti-cancer therapy (3) Date of secondary anti-cancer therapy (4) N/A	Censored Censored Event Ignored
G	Deaths due to reason other than deterioration of 'Study indication'	(1) Date of last adequate assessment	Censored (only TTP and duration of response)

1.=Definitions can be found in [Section 14.1.24](#)
2.=After the last adequate tumor assessment. "Date of next scheduled assessment" is defined in [Section 14.1.25](#).
3.=The rare exception to this is if the patient dies no later than the time of the second scheduled assessment as defined in the protocol in which case this is a PFS event at the date of death.

The primary analysis and the sensitivity analyses must be specified in the protocol. Clearly define if and why options (1) are not used for situations C, E and (if applicable) F.

Situations C (C1 and C2): Progression or death after one or more missing assessments: The primary analysis is usually using options (1) for situations C1 and C2, i.e.

- (C1) taking the actual progression or death date, in the case of only one missing assessment.
- (C2) censoring at the date of the last adequate assessment, in the case of two or more consecutive missing assessments.

In the case of two or missing assessments (situation C2), option (3) may be considered jointly with option (1) in situation C1 as sensitivity analysis. A variant of this sensitivity analysis consists of backdating the date of event to the next scheduled assessment as proposed with option (2) in situations C1 and C2.

Situation E: Treatment discontinuation due to 'Disease progression' without documented progression: By default, option (1) is used for situation E as patients without documented PD should be followed for progression after discontinuation of treatment.

However, option (2) may be used as sensitivity analysis. If progression is claimed based on clinical deterioration instead of tumor assessment by e.g. CT-scan, option (2) may be used for indications with high early progression rate or difficulties to assess the tumor due to clinical deterioration.

Situation F: New cancer therapy given: the handling of this situation must be specified in detail in the protocol. However, option (1), i.e. censoring at last adequate assessment may be used as a default in this case.

Additional suggestions for sensitivity analyses

Other suggestions for additional sensitivity analyses may include analyses to check for potential bias in follow-up schedules for tumor assessments, e.g. by assigning the dates for censoring and events only at scheduled visit dates. The latter could be handled by replacing in [Table 14-5](#) the “Date of last adequate assessment” by the “Date of previous scheduled assessment (from baseline)”, with the following definition:

- **Date of previous scheduled assessment (from baseline)** is the date when a tumor assessment would have taken place, if the protocol assessment scheme was strictly followed from baseline, immediately before or on the date of the last adequate tumor assessment.

In addition, analyses could be repeated using the Investigators’ assessments of response rather than the calculated response. The need for these types of sensitivity analyses will depend on the individual requirements for the specific study and disease area and have to be specified in the protocol or RAP documentation.

14.1.27 Data handling and programming rules

The following section should be used as guidance for development of the protocol, data handling procedures or programming requirements (e.g. on incomplete dates).

14.1.28 Study/project specific decisions

[figure not shown]
For each study (or project) various issues need to be addressed and specified in the protocol or RAP documentation. Any deviations from protocol must be discussed and defined at the latest in the RAP documentation.

The proposed primary analysis and potential sensitivity analyses should be discussed and agreed with the health authorities and documented in the protocol (or at the latest in the RAP documentation before database lock).

14.1.29 End of treatment phase completion

Patients **may** voluntarily withdraw from the study treatment or may be taken off the study treatment at the discretion of the investigator at any time. For patients who are lost to follow up, the investigator or designee should show "due diligence" by documenting in the source documents steps taken to contact the patient, e.g., dates of telephone calls, registered letters, etc.

The end of treatment visit and its associated assessments should occur within 7 days of the last study treatment.

Patients may discontinue study treatment for any of the following reasons:

- Adverse event(s)
- Lost to follow-up
- Physician decision
- Pregnancy
- Protocol deviation
- Technical problems
- Subject/guardian decision
- Death
- Progressive disease
- Study terminated by the sponsor
- Non-compliant with study treatment
- No longer requires treatment
- Treatment duration completed as per protocol (optional, to be used if only a fixed number of cycles is given)

14.1.30 End of post-treatment follow-up (study phase completion)

End of post-treatment follow-up visit will be completed after discontinuation of study treatment and post-treatment evaluations but prior to collecting survival follow-up.

Patients may provide study phase completion information for one of the following reasons:

- Adverse event
- Lost to follow-up
- Physician decision
- Pregnancy
- Protocol deviation
- Technical problems
- Subject/guardian decision
- Death
- New therapy for study indication
- Progressive disease
- Study terminated by the sponsor

14.1.31 Medical validation of programmed overall lesion response

As RECIST is very strict regarding measurement methods (i.e. any assessment with more or less sensitive method than the one used to assess the lesion at baseline is considered UNK) and not available evaluations (i.e. if any target or non-target lesion was not evaluated the whole overall lesion response is UNK unless remaining lesions qualified for PD), these UNK assessments may be re-evaluated by clinicians at Novartis or external experts. In addition, data review reports will be available to identify assessments for which the investigators' or central reader's opinion does not match the programmed calculated response based on RECIST criteria. This may be queried for clarification. However, the investigator or central reader's response assessment will never be overruled.

If Novartis elect to invalidate an overall lesion response as evaluated by the investigator or central reader upon internal or external review of the data, the calculated overall lesion response at that specific assessment is to be kept in a dataset. This must be clearly documented in the RAP documentation and agreed before database lock. This dataset should be created and stored as part of the 'raw' data.

Any discontinuation due to 'Disease progression' without documentation of progression by RECIST criteria should be carefully reviewed. Only patients with documented deterioration of symptoms indicative of progression of disease should have this reason for discontinuation of treatment or study evaluation.

14.1.32 Programming rules

The following should be used for programming of efficacy results:

14.1.33 Calculation of 'time to event' variables

Time to event = end date - start date + 1 (in days)

When no post-baseline tumor assessments are available, the date of randomization/start of treatment will be used as end date (duration = 1 day) when time is to be censored at last tumor assessment, i.e. time to event variables can never be negative.

14.1.34 Incomplete assessment dates

All investigation dates (e.g. X-ray, CT scan) must be completed with day, month and year.

If one or more investigation dates are incomplete but other investigation dates are available, this/these incomplete date(s) are not considered for calculation of the assessment date (and assessment date is calculated as outlined in [Section 14.1.24](#)). If all measurement dates have no day recorded, the 1st of the month is used.

If the month is not completed, for any of the investigations, the respective assessment will be considered to be at the date which is exactly between previous and following assessment. If a previous and following assessment is not available, this assessment will not be used for any calculation.

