Note: Pathologic fracture, new compression fracture, or complications of bone metastases will not be considered as evidence of disease progression, unless one of the above-mentioned criteria is fulfilled.

Table 7-2 Imaging collection plan

Procedure	Screening: Day -21 to -1	Treatment phase	End of treatment
CT or MRI (chest, abdomen, pelvis)	Mandated	Every 10 weeks from treatment start until progression or end of study	Mandated
CT or MRI for any site of disease	Mandated if suspected lesion at screening	If lesion at screening: every 10 weeks from treatment start until progression or end of study	Mandated if lesion at screening
Brain CT or MRI	Mandated at screening only if existing or suspected brain metastases	As clinically indicated	As clinically indicated
Bone scan/X-ray	Mandated	As clinically indicated	As clinically indicated
Bone CT or MRI	Mandated at screening only if skeletal abnormalities identified by bone scan/X-ray at screening	If bone lesion at screening: every 10 weeks from treatment start until progression or end of study	Mandated only if bone lesion at screening
Skin color photography	Mandated if skin lesions at screening	If skin lesions at screening: every 10 weeks from treatment start until progression or end of study	Mandated if skin lesions at screening

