10.6.1.3 Progression-free survival

Progression-free survival (PFS) is the time from date of start of treatment to the date of event defined as the first documented progression or death due to any cause. If a patient has not had an event, progression-free survival is censored at the date of last adequate tumor assessment.

Disease progression will be assessed using the local (treating center's radiologist's) investigator's tumor assessment. PFS will be summarized using the Kaplan-Meier method. Percentiles (25%, median, 75%) of the event time distribution will be presented along with their two-sided 95% confidence interval. The Kaplan-Meier curve will be displayed graphically.

[figure not shown]

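### The missing-month rule in Protocol 14.1.34 can drop a final progression scan and turn a PFS event into a censored time, and its trigger conflicts with the paragraph before it; low impact, but wrong as written

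*Protocol*

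**What the plan says.** Protocol 14.1.34 requires day, month and year for every investigation and then gives three rules.

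- **Some dates incomplete.** "If one or more investigation dates are incomplete but other investigation dates are available", then "this/these incomplete date(s) are not considered for calculation of the assessment date". The assessment date comes from the remaining dates. For a progression assessment, 14.1.24 says "the assessment date is calculated as the earliest date of all measurement dates at that evaluation number".
- **No day on any date.** The first of the month is used.
- **Month missing.** "If the month is not completed, for any of the investigations, the respective assessment will be considered to be at the date" midway between the previous and following assessments. The fallback is: "If a previous and following assessment is not available, this assessment will not be used for any calculation".

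Protocol 10.6.1.3 supplies the consequence for PFS: "If a patient has not had an event, progression-free survival is censored at the date of last adequate tumor assessment".

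On imaging, the treatment-phase column of Table 7-2 has chest, abdomen and pelvis CT or MRI "Every 10 weeks from treatment start until progression or end of study". The end-of-treatment column of the same row also mandates it. Table 7-1 schedules no scan after the end-of-treatment visit.

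**The concern.** The fallback needs an assessment on both sides. An early stable-disease or partial-response scan usually has both, so it is re-dated and kept. The assessment most likely to lack a successor is the one showing progression, because treatment stops there and imaging is scheduled only until then. Whether an observation is lost therefore depends on its outcome, and the loss falls on events.

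The second problem is the trigger. It can mean that no investigation has a month, which fits the first rule. It can also mean that at least one lacks a month, which contradicts it. One evaluation may combine CT or MRI, bone imaging and skin photography, each with its own date, so mixed cases can occur. A programmer has to choose, and the choice can decide between event and censoring.

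PFS is listed as a key secondary endpoint in Table 3-1, and the single arm has no control in which the same error would occur.

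**Working it through.** The documents give no figure that depends on this rule, so there is none to reproduce. I traced one patient through the rules and then sized the effect under assumed frequencies.

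**1. One patient.** Treatment starts 1 January 2014. Scans show stable disease on 12 March and 21 May and progression on 30 July. Protocol 14.1.33 defines time as end date − start date + 1, which gives days 71, 141 and 211. Where a following scan is needed, I assume day 225, two weeks after progression. The midpoint is then (141 + 225) / 2 = 183.

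| Dates at the progression evaluation | Following assessment | Trigger read as: none has a month | Trigger read as: at least one lacks a month |
|---|---|---|---|
| CT dated, bone imaging year only | none | event, day 211 | dropped, censored day 141 |
| CT dated, bone imaging year only | day 225 | event, day 211 | event, day 183 |
| No month on either | none | dropped, censored day 141 | dropped, censored day 141 |
| No month on either | day 225 | event, day 183 | event, day 183 |

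Row 3 is the same under both readings: the event is lost. Row 4 is also the same: the event is kept but dated 211 − 183 = 28 days before the scan. Rows 1 and 2 depend on the reading.

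**2. Does another rule restore the event in row 3?**

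- Table 14-5, situation E: by default, discontinuation for progression without documented progression is ignored.
- A later death counts only if recorded, and at its own later date. Safety follow-up runs to about 30 days after the last everolimus dose.
- If the dropped scan was the only one after baseline, 14.1.24 and 14.1.33 censor the patient at day 1.

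**3. Size on 52-week PFS.** Inputs: exponential PFS with the 7.82-month median that the protocol cites from BOLERO-2; scans every 10 weeks ± 2 weeks; 200,000 simulated patients; follow-up uniform over 30 to 110 weeks (assumed). A share m of progression assessments (assumed) is dropped and the patient censored at the previous scan.

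| m | Share with a PFS event | Kaplan-Meier PFS at 52 weeks |
|---|---|---|
| 0 | 0.703 | 0.342 |
| 1% | 0.696 | 0.345 |
| 2% | 0.689 | 0.348 |
| 5% | 0.668 | 0.358 |
| 10% | 0.633 | 0.374 |

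The increases are about 0.3, 0.6, 1.5 and 3 points. At 5% the rounded table entries differ by 1.6; about 1.5 is the fair reading given rounding and simulation error.

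**4. Size on the median.** A separate simulation used 400 patients, the same median and uniform follow-up of 5 to 25 months (assumed). Dropping 1%, 2%, 5% and 10% loses about 3, 5, 13 and 27 events. The Kaplan-Meier median goes from 8.83 months with no loss to 8.83, 8.95, 9.06 and 9.31.

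**5. Against sampling error.** With 400 patients and ignoring censoring, the 95% half-width at 0.342 is 1.96 × √(0.342 × 0.658 / 400) = 0.046, or 4.6 points.

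**The case against.** The strongest reply is that the section can be read in sequence: some dates incomplete, then all lacking a day, then the month missing as the residual case. On that reading a dated CT beside an undated bone scan gives an event on the CT date and nothing is lost. This stands as a fair reading, so a reader should not infer that one undated investigation always voids a progression assessment. It does not settle the matter: the all-dates case in the preceding rule is worded explicitly as all, while this trigger says any.

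A reader might also infer that the bias always lengthens PFS and that every affected patient loses the event. The documents do not support either. Tables 7-1 and 7-2 require CT or MRI at end of treatment. Where that scan follows the progression scan, the midpoint keeps the event and can date it early, which shortens PFS. A recorded death would still be an event. The documents do not say whether the progression scan may itself serve as the end-of-treatment scan, so both branches remain possible.

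Missing months should be rare. Full dates are mandatory, actual scan dates must be recorded (14.1.8), and the data-capture system runs validation checks and queries (9.3, 9.4). This stands.

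Finally, 14.1.27 calls these rules guidance, and 14.1.28 lets the analysis plan set study-specific decisions. But 14.1.32 says they should be used to program efficacy results. The SAP material available is reporting conventions and output shells, and shows no override. It lists a PFS sensitivity analysis (Table 8.3.3) without visible content.

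**Conclusion.** Wrong as written, low impact. Two things are established from the text: a final progression assessment with no month on any investigation and no successor is dropped and PFS censored at the last adequate scan; and the trigger contradicts the preceding paragraph with no stated precedence. Dropping the event lengthens PFS, while the midpoint branch can shorten it.

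The size rests on an assumed frequency. At 1% to 2% the effect on 52-week PFS is negligible (0.3 to 0.6 points). At 5% it is about 1.5 points, still well inside the 4.6-point sampling margin.

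A much larger effect can be produced and should not be relied on. With the interim BOLERO-2 median of 6.93 months and 5% dropped, the simulated median jumps from 31.8 to 38.3 weeks. That median is about 30.1 weeks, almost on the week-30 scan, so a small shift moves the estimate by a scan interval. With 7.82 months the 5% shift in the separate simulation is 9.06 − 8.83 = 0.23 months, about one week.

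The study is descriptive and its primary endpoint is safety, so no test or primary conclusion is affected.

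**What to change.** Amend 14.1.34, or override it in the SAP, with two sentences:

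1. The missing-month rule applies only when no investigation at that assessment has a usable date (at least month and year). Otherwise the available dates are used, as the preceding paragraph says.
2. When no following assessment exists, the assessment and its response are kept, so progression remains an event. It is dated at the recorded study visit date (SAP Listing 25), no earlier than the previous assessment and no later than the date of last contact.

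The cost is this wording and a small programming change. The downside is that a few assessments carry an approximate date. Midpoint dating stays in place for an undated assessment that has a successor, so reporting how many assessments were dated by each rule would show whether the matter had any effect.
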